PRBC	Packed Red Blood Cells
PSR	Product Surveillance Registry
pfHb	Plasma free hemoglobin
POD	Postoperative Day
PT	Pump thrombosis
PT	Prothrombin Time
RHC	Right heart catheterization
RPM	Revolutions per Minute

Term	Definition
TEE	Transesophageal echocardiogram
TTE	Transthoracic echocardiogram
VAD	Ventricular assist device
VCE	Video Capsule Endoscopy

B. Synopsis

Title	Apogee addendum in Destination Therapy (DT) Post-Approval Study (PAS) patients
Clinical Study Type	Observational, Non-interventional
Product Name and status	The commercially available HeartWare™ HVAD™ System. Approved patient populations, product purpose, indications and uses of the HVAD System and its components and accessories are defined in the product labeling, instructions for use (IFU), or other applicable manuals.
Sponsor	Medtronic
Indication under investigation	This post-market on-label study is intended to collect data from DT subjects who meet the standard criteria for implantation of a Medtronic HeartWare™ HVAD™ System. No new indications are being explored in this study.
Investigation Purpose	The purpose of the Apogee co-enrollment study is to further enhance scientific understanding of the implant procedure, optimized blood pressure management, and anticoagulation / antiplatelet therapies. The goals of Apogee are: 
 • To evaluate collective impact of Apogee standardized guidelines and characterize impact on 12-month aggregate adverse event rate • To better understand the effects of implant technique and patient management on clinical outcomes
Study Design	DT PAS Sites have the option to co-enroll patients in Apogee. Patients must be consented for the DT PAS to be eligible for participation in Apogee, which will require a separate consent. 
Option 1: DT PAS ONLY
  
Option 2: DT PAS with co-enrollment into APOGEE
  
 ▪ The duration of APOGEE is one year post implant; after this all patients continue to be followed under the base DT PAS for a total of five years post implant ▪ All patients at the site are intended to participate in APOGEE although exceptions may occur due to patient non-compliance, etc.
Sample Size	The total sample size will be dependent on the number of sites and patients interested in participation in Apogee. If 1/3 of the total DT PAS patients participate in Apogee, the study would be expected to enroll (but not limited to) ~100 patients (1/3 of the total DT PAS patients since the DT PAS enrolls 300 patients).
Inclusion/Exclusion Criteria	Subjects consented to participate in the DT PAS are eligible for participation in Apogee. There are no exclusion criteria unique to Apogee.

Study Procedures and Assessments	Apogee Data Collection										
			Enroll ment	Baseline	Implant	Discharge	1M F/U	3M F/U	6M F/U	12M F/U	Unsch <12M
	Consent	X									
	Detailed Implant Collection				X						
	Echo for 2D Velocimetry evaluation		X		X 2 TEEs*		X With Lavare On x 5 min & Off x 5 min		X		
	CT Scan Post- implant (send digital image)				X if performed						
	Right Heart Cath (RHC) Hemodynamics		X if subsequent RHC performed						X If performed		
	Chest x-ray (send digital image)				X Post-op						
	Videotape procedure				X if obtained						
	Blood Pressure	Patient BP Diary**					Every morning ≥ 40 minutes after taking BP meds and while sitting. Collect whether HCP contacted for values out of range				
	Medications BP Control						Consider Medication Guidelines; Report Medication Changes				
	Anticoagulation/Antiplatelet	Home INR monitoring					. Collect weekly INR and prescribed Warfarin dosing.				
		VerifyNow Aspirin Assay Laboratory Test	X ≤7 days pre- implant preferred				X	X	X	X	X If seen for bleeding or thrombotic complication
		Enoxaparin bridging and GI Bleed									X angiopoietin- 2 levels if collected
	*Two abbreviated echos are performed in the operating room (OR): 1) TEE in OR after chest is open before going on cardio-pulmonary bypass, and 2) TEE in OR post-implant, after coming off cardio-pulmonary bypass, while chest is still open										
	** Diary includes Doppler pressure, presence of palpable pulse, LVAD parameters, and dizziness symptoms										
Primary Objective	To characterize the 12-month overall major adverse event rate after the collective impact of Apogee standardized protocols and best practices. Major adverse events are defined to be occurrence of infection, bleeding, device malfunction, stroke or death.										
	[REDACTED]										
	[REDACTED]										
	[REDACTED]										
	[REDACTED]										
	[REDACTED]										
	[REDACTED]										
	[REDACTED]										
	[REDACTED]										
	[REDACTED]										

C. Sponsor Contact Information

Sponsor contact information for the study is provided in **Table 1**. Study contact information can be provided separately since this information is subject to change throughout the conduct of the study. Periodic updates to study contact information will be provided to sites as needed.

Table 1: Sponsor Contact Information

US Study Contacts

D. Introduction

D.1. Background

Medtronic is sponsoring the Apogee study. Co-enrollment in Apogee is allowed for patients participating in the Destination Therapy (DT) Post Approval Study (PAS). Patients must be consented for the DT PAS to be eligible for participation in Apogee, which will require a separate consent.

Apogee is conducted within Medtronic's Product Surveillance Registry (PSR) platform and is specific under the DT PAS addendum. The Apogee addendum outlines data collection, applicable procedures, objectives, statistical methodology, analysis cohort, and reporting plans specific to the Apogee study which are not defined in the PSR core and MCS appendix (MCS PSR platform base protocol) or the DT PAS addendum. The combination of these elements together define the requirements for Apogee study.

E. Methodology

E.1. Study Design and Purpose

The Apogee study is a prospective, observational, multi-site study in Destination Therapy (DT) patients. The Apogee study includes three areas of data collection:

- Implant Procedure
- Blood Pressure Management
- Anti-coagulation / Anti-platelet Therapy

Sites choosing to participate in Apogee are expected to collect data in each of these three areas.

Most patients receiving mechanical circulatory support (MCS) experience severe adverse event burden. The 2013 Intermacs report showed that approximately 70% of patients experience a major adverse event within the first 12 months following LVAD implant, with major event defined as the first occurrence of infection, bleeding, device malfunction, stroke or death.¹

Given the heavy adverse event burden, there is an opportunity to understand best practice guidelines. The purpose of Apogee is to further enhance scientific understanding of the implant procedure, optimized blood pressure management, and anticoagulation / antiplatelet therapies. The goals of Apogee are:

- To evaluate the collective impact of Apogee standardized guidelines and characterize impact on 12-month aggregate adverse event rate
- To better understand the effects of implant technique and patient management on clinical outcomes

E.2. Site Participation

It is expected that a subset of the DT PAS sites will participate in Apogee. DT PAS sites can choose to participate in Apogee, or they can decline Apogee and limit their participation to the DT PAS. As an estimate, if one-third of the approximately 50 DT PAS sites participate in Apogee, it is expected the Apogee cohort will be comprised of

¹ Kirklin et al, Fifth INTERMACS annual report: Risk factor analysis from more than 6,000 mechanical circulatory support patients, J Heart Lung Transplant 2013;32:141-156

approximately (but not limited to) 100 patients from approximately (but not limited to) 17 Apogee sites. In general, it is expected that any site participating in Apogee would enroll all of their eligible patients in Apogee; however, there may be exceptions due to timing of Apogee activation, lack of patient interest, or concerns regarding non-compliance.

Prior to enrolling patients in Apogee, sites must be activated in the DT PAS and Apogee and have an established contract, Institutional Review Board (IRB) approval and fulfill any and all other Apogee or IRB initiation requirements. The consent for Apogee is separate from the DT PAS consent. The patient must be consented with the DT PAS consent prior to consenting with the Apogee consent. The study will be conducted in compliance with the protocol, Good Clinical Practice, and the applicable regulatory requirements. The clinical investigation shall be conducted in accordance with the ethical principles that have their origin in the Declaration of Helsinki.

E.3. Enrollment and Duration

The enrollment duration of Apogee is expected to occur parallel to enrollment in the DT PAS. There are no additional inclusion or exclusion criteria to Apogee subjects outside of the requirements outlined in the MCS PSR platform base protocol and the DT PAS Addendum. Full enrollment is anticipated to require approximately 30 months from the date of first DT PAS enrollment and therefore with 12 months of follow-up, total study duration is expected to require 42 months. There is no minimum or maximum number of enrollments per site since data is being used for characterization purposes only.

- Driveline placement and concomitant procedures
- Pump parameters exiting the OR
- Pericardium After Implant

G.2. 2-D Echo Color Doppler Velocimetry

Echos will be collected via digital media and uploaded to Medtronic via secure file transfer (e.g. Box). Medtronic will share echos with the vendor University of California San Diego (UCSD) so they can conduct 2D velocimetry evaluation using their proprietary software to evaluate flow in new ventricular imaging techniques.^{2, 3, 4, 5, 6, 7, 8, 9, 10} The 2D echo color Doppler velocimetry (echo-CDV) modality allows for non-invasive personalized risk assessment of hemolysis and blood clot formation inside the left ventricle. It is hypothesized that this new modality can be used to non-invasively characterize the effect of left ventricular assist device support in LV hemodynamics *in vivo* leading to improved patient care.

The overarching goal is to evaluate the utility of echo-2D color Doppler velocimetry to guide LVAD positioning, pump settings, and minimize the risk for cerebrovascular accident (CVA), pump thrombosis (PT) and hemolysis in the clinical setting. The goals for this work are to:

- Evaluate shear stresses near cannula and their dependence on LVAD pump speed and cannula placement (assess how to minimize hemolysis risk)
- Evaluate changes in blood transport efficiency and blood stasis as a consequence of LVAD placement (assess how to minimize stasis and risk of thrombus formation)
- Evaluate energetic and momentum efficiency created by flow patterns (e.g. flywheel effect) as a potential outcome predictor

Echocardiograms will be obtained when performed per standard institutional procedures, which is expected to occur at the following timepoints:

- Baseline (prior to implant) – transthoracic echocardiogram (TTE)
- In OR, after chest is open prior to cardio-pulmonary bypass and prior to implantation - transesophageal Echocardiogram (TEE)
- In OR, after implantation, off cardio-pulmonary bypass, while chest is still open- transesophageal Echocardiogram (TEE)
- Prior to Discharge (capture with Lavare off for 5 minutes*)- transthoracic echocardiogram (TTE)
- Prior to Discharge (capture with Lavare turned on for 5 minutes*)- transthoracic echocardiogram (TTE)
- 3 months post-implant - transthoracic echocardiogram (TTE)

Echo data will also be collected on a Case Report Form (CRF).

Apogee sites will manage blood pressure according to blood pressure management guidelines described in the DT PAS PSR platform addendum and the product labeling, which may include but is not limited to the IFU and the product reference manuals. In addition, Apogee sites will report items from the patient diary and consider medication guidelines for hypertensive patients. The patient will check whether they have a palpable pulse at each check. Diary recordings will be entered into the CRF, including Doppler pressure, presence of palpable pulse, LVAD measurements and presence of dizziness.

Inpatient Medication Guidelines	
1.	Manage to target goal: 75-90 mmHg (via Doppler/cuff method once arterial line pulled)
2.	Ensure patient and caregiver(s) properly trained on Doppler/cuff method prior to discharge
3.	Medication guideline recommendations for management of hypertensive patients prior to discharge: In patients without AKI or significant renal dysfunction: 
• First line therapy: Angiotensin converting enzyme inhibitor (ACE-I) or Angiotensin II receptor blocker (ARB)

- Second line therapy: Nitrates and/or Hydralazine, spironolactone, or Norvasc* (Amlodipine)

- Third line therapy: Clonidine

[figure not shown]
In patients with AKI or significant renal dysfunction:

- First line therapy: Nitrates and/or Hydralazine or Norvasc* (Amlodipine)
- Second line therapy: Clonidine

[figure not shown]
*Note: Norvasc (Amlodipine) will not acutely lower blood pressure

In-patient Blood Pressure Management Algorithm

Patients WITHOUT AKI or significant renal dysfunction:

Patients WITH AKI or significant renal dysfunction:

*Note: Norvasc (Amlodipine) will not acutely lower blood pressure

Outpatient Diary Collection & Medication Guidelines

Blood pressure monitoring (using Doppler with cuff)

[figure not shown]
- Time of day: Measure every morning at least 40 minutes AFTER taking BP medication and during resting conditions, while sitting
- Frequency: Measure daily. If stable after 1 month of daily monitoring, Investigator can consider reducing frequency to measuring 3 times per week (e.g., every Monday/Wednesday/Friday schedule). Stable is defined as: no instances of BP>90 mmHg for three consecutive days and not a single occurrence of BP>110 mmHg (i.e. no instances of needing to call HCP)
- Diary: Patient to record Doppler pressure, presence of palpable pulse or dizziness, and HVAD measurements from controller (i.e. power, flow, RPM, peak, trough) in diary and bring to site during scheduled visits. Site will record these onto CRF.

Patient should call site if:

- BP >90 for 3 consecutive days or if postural symptoms >48 hours (e.g. orthostatic reaction)
- BP >110 for single timepoint (take BP measurement twice before calling to confirm both show >110 at timepoint)
- BP <60 for single timepoint (take BP measurement twice before calling to confirm both show <60 at timepoint)
- Patients with symptoms of hypotension (dizziness/syncope/presyncope/weakness) should be instructed to call even if values read normal.

Medication guidelines for hypertensive patients post discharge

- See algorithm

I. Anti-Coagulation / Platelet Therapy Investigation

I.1. Aspirin Management Plan

The site will be asked to report the patient's aspirin dose and dose start date at discharge and throughout follow-up or when the patient presents with a bleeding or thrombotic event, including hemorrhagic or ischemic strokes. Per the HeartWare HVAD System Instructions for Use, "In general, aspirin should be started at doses >81 mg/day" (i.e., moderate-dose aspirin of 162mg or high-dose of 325mg, etc.). The Medication Log captures aspirin dose and any changes.

I.2. VerifyNow Aspirin Assay Laboratory Test

A VerifyNow Aspirin Assay and CBC (if available) will be collected along with the current aspirin dose and its start date at each scheduled follow-up visit through 12 months. The assay and CBC (if available) will also be collected at all Unscheduled Visits, if the patient presents with a bleeding or thrombotic complication, including hemorrhagic or ischemic strokes. See Appendix A for instructions on the use of the VerifyNow Aspirin assay, which is also available online at <http://www.accumetrics.com/products/verifynow-system-platelet-reactivity-test>.

The purpose of collecting this information is to correlate the VerifyNow Assay results with bleeding or thrombotic events. Information from the assay collection may characterize the platelet reactivity and responsiveness to aspirin in patients supported by the HeartWare HVAD System, up to one-year post-implant. It may also characterize whether platelet activity is greater in ventricular assist device (VAD) patients with frequent/severe thrombotic events as compared to those with less frequent/less severe thrombotic events, and

also whether levels of platelet activity/reactivity are reduced in VAD patients with hemorrhagic events compared to those without such events.

During this study, sites should continue to follow their current institutional practice and IFU recommendations for aspirin dose adjustments. Test results from the VerifyNow Assay should not be used to guide aspirin dosing unless this is the center's current standard of practice.

I.3. Home INR Monitoring

The HVAD IFU recommends anticoagulation with the recommended INR range of 2.0 – 3.0. Home INR monitoring will be instituted with point of care testing for subjects on anticoagulation therapy with intent to improve time in therapeutic range. Where possible, INR monitoring equipment will be provided to subjects for weekly INR monitoring. Sites will record reported INR values.

The anticoagulation management strategy/protocol will be site defined. Sites should use a warfarin management software as part of the dosing algorithm (sites can follow their VAD center protocol and manage warfarin dosing using their preferred software algorithms). Any suspected stroke should be confirmed with CT scan.

I.4. Enoxaparin Bridging Recommendation (for stable ambulatory patients with sub-therapeutic INR)

It is recommended that ambulatory patients with an INR \leq 1.7 be bridged with enoxaparin (or fondaparinux) unless contraindicated, such as increased risk of bleeding. Details of data collection and enoxaparin bridging recommendations include:

- Collect previous history of gastrointestinal (GI) bleeding, presence of nasal arteriovenous malformation (AVM), proton pump inhibitor (PPI) use, bleeding location (upper/ lower / small bowel bleed), and any endoscopic procedure(s) findings such as video capsule endoscopy (VCE) and enteroscopy
- Enoxaparin Dosing: For eGFR > 30 -- 1mg per kg bid rounded to the nearest 10mg
- Dosing may be altered for patients with increased risk of bleeding where half-dose dosing may be considered (0.5mg/kg)
- A patient should meet the following criteria to receive enoxaparin bridging:
 - Minimum weight: women must weigh more than 45 kg; men more than 57 kg
 - Most recent platelet count > 100,000/UL
 - Ability to safely and accurately self-administer enoxaparin
- In a patient with a contraindication to enoxaparin, fondaparinux can be utilized:
 - Fondaparinux 7.5mg SC daily (wt 50-100kg)
 - Fondaparinux 10mg SC daily (wt > 100mg)

I.5. GI bleeding Recommendation

Subject management strategies for GI bleeding (GIB) have recently been described, including an endoscopic algorithm to eliminate sequential and overlapping procedures, and to eliminate low-yield procedures;¹¹ This algorithm was focused on maximizing procedures with the highest diagnostic and therapeutic yields while

¹¹ Axelrad et al, Limited usefulness of endoscopic evaluation in patients with continuous-flow left ventricular assist devices and gastrointestinal bleeding. J Heart Lung Transplant 2018;37:723–732

minimizing low-yield procedures or procedures without therapeutic potential. **Table 3** shows the recommended algorithm, adapted from Axelrad 2018 et al.¹¹

Table 3: Proposed endoscopic algorithm for the management of GIB¹¹

	If Upper GI Bleed Source Suspected	If Lower GI Bleed Source Suspected	If Occult GI Bleed
Signs / Symptoms	Melena, coffee-ground emesis, hematemesis	Hematochezia	Hemepositive brown stool, iron deficiency anemia
Suggested Actions	Push Enteroscopy (PE) as first endoscopic procedure rather than EGD with sequential push enteroscopy	Colonoscopy	
 Initial medical management with blood products and/ or temporary reduction or withholding of anti-thrombotic therapy followed by push enteroscopy if major bleeding occurs as defined by the replacement of >2 units of pRBC over a 48-hour period 
For all patients, propose further endoscopic evaluation for:
 
 Hemodynamic instability or continued GIB despite administration of blood products Persistent GIB despite withholding or after resumption of lower dose anti-thrombotic therapies Age-appropriate colon cancer screening

Diagnostic testing for GI bleeds will be collected. If acquired by the center due to recurrent GI bleeding, angiopoietin-2 levels will be collected.

J. Objectives and Statistical Methodology

General Considerations

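### The upper fondaparinux weight band in Protocol section I.4 is printed in milligrams, so as written it overlaps the whole of the 50-100 kg band and takes in patients below 50 kg

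*Protocol*

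**What the plan says.** Protocol section I.4 is headed as a recommendation on enoxaparin bridging for stable ambulatory patients whose INR is below range. It opens: "It is recommended that ambulatory patients with an INR \leq 1.7 be bridged with enoxaparin (or fondaparinux) unless contraindicated, such as increased risk of bleeding".

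It then lists conditions for receiving enoxaparin, one of them a body weight in kilograms: "Minimum weight: women must weigh more than 45 kg; men more than 57 kg".

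For those who cannot have enoxaparin it says: "In a patient with a contraindication to enoxaparin, fondaparinux can be utilized". Two lines follow, each pairing a dose with a weight band:

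- "Fondaparinux 7.5mg SC daily (wt 50-100kg"
- "Fondaparinux 10mg SC daily (wt > 100mg"

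The SAP text available does not restate these lines. The addendum version history in Protocol section M does not mention them.

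**The concern.** The two lines appear to be meant as separate weight bands that between them select a dose, but they do not share a unit. A body-weight limit of 100 mg excludes nobody, so the second line cannot act as an upper band. Taken literally, the text gives two answers for some patients and, for the lightest, points to the higher of the two listed doses.

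What is at stake is the clarity of dosing guidance for an anticoagulant in patients with a ventricular assist device. Many prescribers would probably notice the slip, but a dose-selection criterion should not depend on that. The Apogee recommendations are also what the study sets out to characterize, so their text should be right in the record.

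**Working it through.** No figure in the plan needs reproducing here. The check is a unit conversion, followed by a test of which printed conditions a given body weight meets.

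**Inputs, all from Protocol section I.4**

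- 7.5 mg line: weight from 50 to 100 kg (both ends taken as included).
- 10 mg line: weight above 100 mg, as printed.
- Other body weights in the same list: minimum weights for enoxaparin of 45 kg (women) and 57 kg (men).

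**Step 1, conversion.** 1 kg = 1,000,000 mg, so 100 mg = 100 / 1,000,000 = 0.0001 kg. A patient of 50 kg weighs 50,000,000 mg. Every patient exceeds the printed limit.

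**Step 2, which lines are met as printed**

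| Body weight | Weights tested (kg) | 7.5 mg line | 10 mg line | Both |
|---|---|---|---|---|
| Below 50 kg | 40, 45, 49.9 | no | yes | no |
| 50 to 100 kg | 50, 57, 75, 100 | yes | yes | yes |
| Above 100 kg | 100.1, 120, 150 | no | yes | no |

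The overlap is the whole of the 50 to 100 kg band and nothing outside it.

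**Step 3, size of the conflict.** 10 / 7.5 = 1.33, so the second listed dose is one third higher than the first.

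**Step 4, the lightest patients.** The documents do not say whether falling short of the enoxaparin minimum weights counts as a contraindication to enoxaparin. If a site reads it so, low weight is itself a route to these two lines. As printed, a woman at or below 45 kg would then meet only the 10 mg line. A man at or below 57 kg would meet only the 10 mg line if under 50 kg, and both lines from 50 to 57 kg.

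**Step 5, is the unit the source of the conflict?** For illustration only, the same weights were tested with the second limit read in the unit of the first. No tested weight then meets both lines, and those below 50 kg meet neither. The overlap therefore comes from the unit alone. This does not show which rule the sponsor intends.

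**The case against.** The strongest case on the other side is that this is a one-letter slip. The adjacent line and the minimum weights are in kilograms, nobody records body weight in milligrams, and a prescriber is unlikely to apply the line literally. The guidance is also optional: section I.4 recommends and permits, section I.3 leaves the anticoagulation strategy to each site, and the synopsis describes an observational, non-interventional study. All of this stands, and it limits the severity. It does not make the printed threshold correct.

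The second objection is timing. SAP section 3 says that new implants stopped on 03-Jun-2021 with all patients already enrolled, and Apogee follow-up lasts one year after implant. On those dates follow-up would end by about June 2022, and the SAP's own reference list includes a January 2022 publication. A notice to sites may have little audience left. That also stands.

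The documents do not support three stronger readings:

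- A reader might infer that every patient qualifies for both doses. Every patient meets the 10 mg line, but only those of 50 to 100 kg also meet the 7.5 mg line.
- A reader might infer that this is a mandated study dose. It is an option for a narrow group.
- Because the primary composite includes major bleeding and stroke, a reader might infer that the primary result is compromised. The documents do not say how many of the 124 co-enrolled patients (SAP section 5.2) received fondaparinux, so no effect on event rates can be derived from them.

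A last caveat: the text was extracted by program from a PDF, so a misread letter cannot be wholly excluded. The line otherwise reads cleanly, and the kilogram unit just above it came through correctly.

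**Conclusion.** The point holds as an internal inconsistency in dosing guidance. As printed, every patient meets the 10 mg line, patients of 50 to 100 kg meet both lines with listed doses one third apart, and patients below 50 kg meet only the 10 mg line.

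Severity is minor. The primary analysis in SAP section 7.9.1 is a descriptive Kaplan-Meier estimate of time to first major adverse event. Its events, time origin and censoring rules make no reference to bridging doses, and no hypothesis test or sample size depends on them. The ancillary objectives are redacted, so nothing is claimed about them. The reason to act is safety and an accurate record, at almost no cost.

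The conclusion assumes that the extracted text matches the PDF and that no separate site communication, outside the documents reviewed, has already corrected the line.

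**What to change.** First check the line against the source PDF. The sponsor should then confirm from its own source what the two lines were meant to say, since section I.4 cites none for them. It should reconcile them so that they use one body-weight unit and do not conflict, and state how patients below 50 kg are meant to be handled by this text. The protocol text should be corrected, and any site still following Apogee patients or reusing the guidance should be told. This review proposes no dose and no cut-off.

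The cost is a correction to a line or two of the protocol and, where a site is still affected, a short notice. No SAP change, re-analysis or new data collection is needed.
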